# 1.6. Comparator Drug

The control treatment in this study consists of the bPI regimen DRV/COBI FDC (see Section 1.3) coadministered with FTC/TDF FDC (TVD).

## Truvada® (Emtricitabine/tenofovir disoproxil fumarate FDC)

For information on FTC, see Section 1.4. TDF is a first generation oral prodrug of TFV that has been studied extensively in clinical studies for the treatment of HIV-1 infection and has demonstrated antiviral activity against both wild-type and nucleoside resistant strains of HIV-1. Under the trade name Viread®, TDF is marketed by GSI as a once-daily tablet (300 mg) and as a powder (1 g contains 40 mg TDF). TDF has also been coformulated and marketed in several coformulations with other HIV-1 ARV drugs, such as FTC/TDF FDC (TVD). TVD, in combination with other ARVs, is indicated for the treatment of HIV-1 infection in adults and in pediatric patients 12 years of age or older.

The most frequently reported adverse reactions considered possibly or probably related to FTC and/or TDF were nausea (12%) and diarrhea (7%) in an open-label, randomized clinical trial (GS-01-934). The safety profiles of FTC and TDF in this study were consistent with the previous experience with these agents when each was administered with other ARV agents. 32,36

For further information regarding TDF and FTC/TDF FDC, refer to the Prescribing Information for TDF and FTC/TDF FDC. 32,33,36,37

## 1.7. Overall Rationale and Risks Assessment for the Study

The success of HAART and the apparent benefits of maximally suppressed viremia have shifted clinical attention towards ARV agents that optimize long-term safety and tolerability. This medical need becomes clearer as the HIV-positive population ages; morbidity and mortality are increasingly driven by non-AIDS associated comorbidities, and these age-associated comorbidities are observed earlier than in the non-HIV-1 infected population despite the best current chronic therapy.  In addition, young, newly infected patients are diagnosed earlier, initiate therapy earlier, and look ahead towards lifelong therapy, often more than 50 years. 

Incomplete adherence to ARV regimens is a critical factor contributing to the development of viral resistance and treatment failure and is thus a primary barrier to successful long-term treatment. Studies have shown that once-daily single-tablet regimens improve adherence, treatment satisfaction, and virologic outcomes for patients infected with HIV-1. 1,10,14,18 Due to a longer duration of high adherence, patients taking single-tablet regimens also have better clinical outcomes, such as fewer hospitalizations, when compared with multiple pill regimens. 27

To improve care for HIV-infected patients and maximize tolerability, safety, clinical efficacy, and adherence, the sponsor is developing DRV with COBI, FTC and TAF into a FDC tablet (D/C/F/TAF). This new formulation would provide an additional single tablet option, in particular for subjects requiring PI-based regimens, and would be an attractive new once-daily

simplified regimen. The D/C/F/TAF FDC tablet also represents a new alternative for individuals intolerant to currently available combination tablet regimens, and may promote better adherence to bPI-based regimens. Additionally, compared with TDF, the use of TAF in the D/C/F/TAF FDC tablet is postulated to provide greater delivery to lymphatic tissues of TFV and higher intracellular levels of the active phosphorylated moiety TFV-DP, more effective suppression of residual viral replication in a wider range of reservoir and anatomic sanctuaries of HIV, greater and faster viral load reduction during initial therapy, and lower systemic levels of TFV.

The principal anticipated drug-drug interaction upon administration of the 4-drug combination is the intended inhibition of CYP3A activity by COBI and the consequent increase in DRV exposure to levels similar to those observed using rtv as a boosting agent. The DRV/COBI 800/150 mg once-daily regimen with other ARV agents has already been established for use in HIV-1 infected patients. DRV and COBI concentrations are not anticipated to be affected by FTC or TAF. For TAF regimens including a pharmacokinetic enhancer (rtv or COBI), a 10 mg dose TAF is used as opposed to a TAF 25 mg dose currently in development for use with other (non-boosted) ARV agents (see also Section 3.3).

Administration of DRV with COBI as a pharmacokinetic enhancer, FTC, and TAF in a single tablet is not expected to change the antiviral activity and, by extension, the resistance profiles of DRV, FTC, and TAF.

The combination of D/C/F/TAF is not anticipated to exacerbate known toxicities or lead to new toxicities compared to DRV/COBI FDC coadministered with FTC/TDF FDC. DRV and FTC have established clinical safety profiles with no significant toxicities observed. Liver toxicity related to COBI, which was observed preclinically, has not been observed clinically to date. Standard liver enzyme assays will be used to monitor for these potential adverse effects. Minimal mononuclear cell infiltration in the posterior uvea has been observed at the highest dose of TAF (12 to 18 mg/kg) in dogs. More than 3,000 HIV-positive subjects have been exposed to TAF as part of the Phase 2 and 3 E/C/F/TAF clinical development program by GSI and no AEs consistent with posterior uveitis in humans have been reported. Nonetheless, if subjects develop signs or symptoms of posterior uveitis, which include notable eye pain or redness, reduced visual acuity, or "floaters", investigators in this study should inform the sponsor's medical monitor and determine, based on their medical judgment, the need for ophthalmologic evaluation including dilated fundoscopy, and if required, optical coherence tomography.

The primary nonclinical toxicities for TAF are renal and bone toxicity. Based on available data from the ongoing COBI and E/C/F/TDF tablet clinical development programs, decreases in eGFR are anticipated due to the known effects of COBI on the renal tubular excretion of creatinine, without an impact on the renal glomerular function. Studies GS-US-292-0102 and GS-US-236-0118 showed that the E/C/F/TDF tablet, as well as ATV/COBI or DRV/COBI + background regimens were safe and well tolerated in subjects with mild renal impairment (eGFR 50 to 89 mL/min). The combination of D/C/F/TAF is not anticipated to have an effect on actual glomerular filtration rate, monitoring of creatinine along with other standard clinical tests for renal and bone disorders is planned in all clinical studies with the

D/C/F/TAF FDC tablet. The eligibility criteria for study TMC114FD2HTX3001 with the D/C/F/TAF FDC tablet allow the inclusion of subjects with a screening eGFR of ≥70 mL/min. Changes from baseline in serum creatinine, in eGFR based on creatinine clearance (eGFRcreatinine) and in eGFR based on cystatin C clearance (eGFRcystatin C) will be measured in this study. In addition, a renal management algorithm to optimally evaluate and determine the benefit/risk balance for continued participation of subjects whose eGFRcreatinine would decrease <50 mL/min is also included in the study protocol. As recent data suggest that the combined use of COBI and TDF might increase proteinuria (expected to be less with TAF), this study will also assess the effects of the D/C/F/TAF FDC tablet on proteinuria, albuminuria, beta-2-microglobulinuria, and urine retinol-binding protein (RBP).

In addition, assessment of bone mineral density (BMD) is included in the study protocol as a substudy, and follow-up per local medical practice at the discretion of the investigator will be recommended in case a decrease from baseline of >7% in the hip region or >5% in the spine region is demonstrated. Selected bone biomarkers, including C-type collagen sequence (CTX), procollagen type N-terminal propeptide (P1NP), parathyroid hormone (PTH), and 25-hydroxy vitamin D, will be monitored in the substudy.

Two clinical studies to date have been performed with the D/C/F/TAF FDC tablet regimen (GS-US-299-0101 in healthy volunteers [N=102], and GS-US-299-0102 in ARV treatment-naïve HIV-1 infected subjects [N=153]). No new or unexpected adverse drug reactions were identified in these studies.

The aim of study TMC114FD2HTX3001 is to evaluate the efficacy and safety of the D/C/F/TAF FDC tablet in ARV treatment-naïve HIV-1 infected subjects. The active control in this randomized, double-blind, comparative study is DRV/COBI FDC coadministered with FTC/TDF FDC.

Week 48 is the primary analysis time point. An additional analysis will be performed when all subjects have completed the Week 96 visit or discontinued earlier. Final analysis will be conducted when all subjects have completed the extension phase or discontinued earlier (see also Section 3.1).

### 2. OBJECTIVES AND HYPOTHESIS

### 2.1. Objectives

## **Primary Objective**

The primary objective is to demonstrate noninferiority in efficacy of a D/C/F/TAF FDC tablet versus DRV/COBI FDC coadministered with FTC/TDF FDC in HIV-1 infected, ARV treatment-naïve adult subjects, as determined by the proportion of virologic responders defined as having HIV-1 RNA <50 copies/mL at Week 48 (FDA-defined snapshot analysis), with a maximum allowable difference of 10%.

### **Secondary Objectives**

The secondary objectives of this study are:

- To evaluate superiority of a D/C/F/TAF FDC tablet versus DRV/COBI FDC coadministered with FTC/TDF FDC as determined by the proportion of virologic responders defined as having HIV-1 RNA <50 copies/mL at Week 48 (FDA-defined snapshot analysis), in case noninferiority is established;
- To evaluate the immunologic response (CD4+ cell count) of the 2 treatment arms through Week 48;
- To evaluate the incidence of grade 3 and 4 AEs, serious adverse events (SAEs), and premature discontinuations due to AEs in the 2 treatment arms through Week 48;
- To evaluate the change from baseline in serum creatinine, eGFRcreatinine (by Cockcroft-Gault and by Chronic Kidney Disease Epidemiology Collaboration [CKD-EPI] formulas) and eGFRcvstatin C (by CKD-EPI) in the 2 treatment arms at Week 48;
- To evaluate the change from baseline in renal biomarkers at Week 48;
- To assess the development of viral resistance in the 2 treatment arms through Week 48;
- To evaluate the steady-state pharmacokinetics of DRV and TAF;
- To evaluate long-term efficacy, resistance, and safety of the D/C/F/TAF regimen (Week 96 and beyond).

Objectives of a bone investigation substudy performed at selected study sites:

- To evaluate the safety in the 2 treatment arms as determined by the percentage change from baseline in hip and spine BMD and change from baseline in T-score at Week 48;
- To evaluate the change from baseline in bone biomarker levels at Week 48.

### 2.2. Hypothesis

Null hypothesis: D/C/F/TAF FDC is inferior to DRV/COBI FDC coadministered with FTC/TDF FDC by at least 10% with respect to the proportion of subjects having HIV-1 RNA <50 copies/mL at Week 48 (as defined by the FDA-defined snapshot analysis).

Alternative hypothesis: D/C/F/TAF FDC is noninferior to DRV/COBI FDC coadministered with FTC/TDF FDC by less than 10% with respect to the proportion of subjects having HIV-1 RNA <50 copies/mL at Week 48 (as defined by the FDA-defined snapshot analysis).

#### 3. STUDY DESIGN AND RATIONALE

### 3.1. Overview of Study Design

This is a 96-week multicenter, Phase 3 study consisting of a 48-week randomized, double-blind active-controlled treatment period, to evaluate a D/C/F/TAF FDC tablet versus DRV/COBI FDC coadministered with FTC/TDF FDC in ARV treatment-naïve HIV-1 infected adult subjects,

followed by an open-label single-arm D/C/F/TAF treatment period for all subjects up to Week 96 to asses long-term efficacy, resistance, and safety.

A target of 670 subjects will be randomly assigned in this study with 335 subjects planned per treatment arm.

Prior to or at the baseline visit (Day 1), subjects who meet all eligibility criteria will be randomized in a 1:1 ratio to 1 of the following 2 treatment arms:

- D/C/F/TAF Arm: Regimen of a single tablet containing DRV 800 mg/ COBI 150 mg/

FTC 200 mg/ TAF 10 mg (D/C/F/TAF FDC) once daily, (n=335)

+ DRV/COBI FDC-matching and FTC/TDF FDC-matching placebo

tablets once daily;

- Control Arm: Regimen of DRV 800 mg/ COBI 150 mg FDC coadministered with FTC

200 mg/ TDF 300 mg FDC once daily, (n=335)

+ D/C/F/TAF FDC-matching placebo tablet once daily.

Randomization will be stratified by HIV-1 RNA level ( $\leq 100,000$  copies/mL or > 100,000 copies/mL) and CD4+ cell count (< 200 cells/ $\mu$ L or  $\geq 200$  cells/ $\mu$ L) at screening.

Subjects will be treated for 96 weeks, and will return for study visits at Weeks 2, 4, 8, 12, 24, 36, 48, every 12 weeks thereafter until and including a Week 96 visit.

After Week 48, subjects will continue to take their blinded study drug and attend visits every 12 weeks until all subjects have reached Week 48, the database for the primary analysis has been locked, and treatment assignments have been unblinded. Provided the results from the primary analysis do not preclude (further) exposure of subjects to D/C/F/TAF, all subjects will return for an unblinding visit and will receive the D/C/F/TAF FDC tablet treatment during an open-label single-arm treatment phase up to Week 96. Subjects from the control arm who switch to the D/C/F/TAF regimen after the 48-week double-blind treatment will be required to return to the clinic for an additional visit 3 to 7 weeks after the unblinding visit.

After Week 96, subjects will be given the opportunity to continue D/C/F/TAF treatment during an extension phase until the D/C/F/TAF FDC tablet becomes commercially available and is reimbursed, or can be accessed through another source in the country where he/she is living, or until the sponsor terminates clinical development. During the extension phase subjects will attend visits every 6 months.

Subjects who prematurely discontinue, either during the double-blind treatment phase (from Day 1 to Week 48) or during the single-arm D/C/F/TAF phase (between Week 48 and Week 96) will be required to return to the clinic within 72 hours of stopping study treatment for the early study treatment discontinuation (ESTD) visit.

In addition, a 30-day follow-up (FU) visit will be required for any subject who has an ongoing AE or serious adverse event (SAE) at the time of his/her last study visit (unless consent is withdrawn).

Thus, the study will include a screening period of approximately 30 days (up to maximum 6 weeks) starting from the signature of the informed consent form (ICF), double-blind active-controlled treatment for at least 48 weeks, an open-label single-arm D/C/F/TAF treatment up to Week 96 and an extension phase. A 30-day FU visit may take place as described above.

The primary analysis of this study will be performed when all subjects have completed the Week 48 visit or discontinued earlier. An additional analysis will be performed when all subjects have completed the Week 96 visit. The final analysis will be performed once all subjects have completed the extension phase (and the 30-day FU visit if applicable), or discontinued earlier.

The safety and tolerability, as well as efficacy, of the enrolled subjects and treatment regimens will be monitored by an independent Data Monitoring Committee (DMC). Refer to Section 11.8 for details. In addition to the Week 48, Week 96, and final analyses, formal DMC analyses will be performed for monitoring purposes, including a futility analysis for lack of (non-inferior) efficacy and a blinded sample size re-estimation.

A diagram of the study design is provided in Figure 1.

Assessment and reporting of drug adherence and accountability, concomitant medications, and AEs, laboratory evaluations for efficacy and safety (viral load, CD4+ cell count, biochemistry, hematology, urinalysis, urine chemistry), vital signs and (complete or symptom-directed) physical examinations will be performed at each visit, except for drug accountability at Week 2. At screening, a 12-lead electrocardiogram (ECG) and an HIV-1 genotype test will be performed. Urine for assessments of selected renal biomarkers, including RBP and beta-2-microglobulin, will be collected at baseline and at the time points specified in the Time and Event Schedule.

Screening genotype testing will be performed for all subjects to assess sensitivity to DRV, TDF and FTC. Further HIV-1 PR and RT genotype/phenotype testing will be performed at later time points for subjects that are eligible for resistance testing (subjects with virologic rebound, virologic nonresponse, and discontinuations with last available viral load measurement ≥400 copies/mL). If resistance to the study drugs is documented, study drugs may be discontinued.

Pharmacokinetic assessments (sparse sampling) will be performed for all subjects (single sample from Weeks 4 through 48 or the ESTD visit, except at Weeks 8 and 36 visits, when 2 samples will be collected ≥2.5 hours apart).

A bone investigation substudy will be performed at selected study sites, to assess bone biomarkers and dual energy x-ray absorptiometry (DXA) scans, in at least 170 subjects (85 subjects in each treatment arm) who provide informed consent for the substudy.

To determine BMD of the hip and spine, consenting subjects will have DXA scans performed at the time points specified in the Time and Event Schedule. In subjects participating in the DXA substudy, blood will be collected for assessment of bone biomarkers at the time points specified in the Time and Event Schedule.

Figure 1:	Schematic	Overview	of the Study
-----------	-----------	----------	--------------

Base (Day		k 24 Week AC b Primary a		Veek 96 e Analysis	
Screening	Double-Blin	d Treatment Phase f	Single-arm Treatment Phase c,d,f	Extension Phase e	Follow-up
≤30 days prior to baseline	matching placebo to Treatment arm 2 (Co DRV/COBI FDC of FDC once dailyg	once daily g matching and FTC/TDF FDC- tablets once daily g	D/C/F/TAF FDC	D/C/F/TAF FDC	ESTD f and 30-day FU visit h

- a Following the baseline visit, subjects will return for study visits at Weeks 2, 4, 8, 12, 24, 36, 48, and every 12 weeks thereafter until and including a Week 96 visit.
- Formal DMC interim analyses will be performed for monitoring purposes, including a futility analysis for lack of (non-inferior) efficacy and a blinded sample size re-estimation.
- c Subjects will continue to take their blinded study drug and to attend visits every 12 weeks following Week 48 until treatment assignment is unblinded.
- After unblinding, provided the results from the primary analysis do not preclude (further) exposure of subjects to D/C/F/TAF, all subjects will receive D/C/F/TAF treatment during a single-arm treatment phase up to Week 96. Subjects from the control arm who switch to the D/C/F/TAF regimen after the 48-week double-blind treatment will be required to return to the clinic for an additional visit 3 to 7 weeks after the unblinding visit.
- After Week 96, subjects will be given the opportunity to continue D/C/F/TAF treatment during an extension phase until the D/C/F/TAF FDC tablet becomes commercially available and is reimbursed, or can be accessed through another source in the country where he/she is living, or until the sponsor terminates clinical development. During the extension phase subjects will attend visits every 6 months.
- Subjects who prematurely discontinue, either during the double-blind treatment phase (from Day 1 to Week 48) or during the single-arm D/C/F/TAF treatment phase (between Week 48 and Week 96) will be required to complete the ESTD assessments within 72 hours of stopping study treatment.
- All study drugs and matching placebo tablets must be administered orally, once daily in the morning with food, at approximately the same time each day.
- Any subject who has an ongoing AE or SAE at the time of his/her last study visit will be required to return to the clinic 30 days after the completion their his/her study visit for a 30-day FU visit (unless consent is withdrawn).

# 3.2. Study Design Rationale

### Control, Blinding, Randomization and Stratification

A bPI in combination with 2 NRTIs, an established regimen for treatment-naïve HIV-infected patients, is the active control treatment in this study. The active control treatment consists of the DRV/COBI FDC (PREZCOBIX/REZOLSTA) coadministered with FTC/TDF FDC (TVD). In addition, since TAF is substituted by TDF in the comparator treatment, the active control treatment will allow a direct comparison of these 2 ARVs for safety assessments.

Blinded treatment will be used to reduce potential bias during data collection and evaluation of clinical endpoints.

Randomization will be used to minimize bias in the assignment of subjects to treatment arms, to increase the likelihood that known and unknown subject attributes (eg, demographic or baseline characteristics) are evenly balanced across treatment arms, and to enhance the validity of statistical comparisons across treatment arms. Equal randomization will be done because this requires a lower total sample size to attain the same power versus randomization with unequal division.

Two stratification factors (HIV-1 RNA level [ $\leq$ 100,000 copies/mL or >100,000 copies/mL] and CD4+ cell count [<200 cells/ $\mu$ L or  $\geq$ 200 cells/ $\mu$ L] at screening) will be applied in the randomization process and will subsequently be used in the statistical analysis as covariates in the models. Since previous publications have shown that baseline viral load can be a predictive factor for outcome, this will ensure a balanced distribution of subjects across treatment arms.  $^{11,15}$ 

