#### 11. STATISTICAL METHODS

Statistical analysis will be done by the sponsor or under the authority of the sponsor. A general description of the statistical methods to be used to analyze the efficacy and safety data is outlined below. Specific details will be provided in the Statistical Analysis Plan.

The following analyses will be performed:

- Formal independent DMC analyses for monitoring purposes, including a futility analysis for the lack of (non-inferior) efficacy and a blinded sample size re-estimation (see also Section 11.8).
- The primary analysis: once all subjects have completed the Week 48 assessments or discontinued earlier.
- The Week 96 analysis: once all subjects have completed the Week 96 assessments or discontinued earlier.
- The final analysis: once all subjects have completed the extension phase and the 30-day FU visit (if applicable), or discontinued earlier.

Additional statistical analyses may be done as needed to prepare for interactions with regulatory authorities.

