# 11.4. Efficacy Analyses

## 11.4.1. Primary Analysis

The primary analysis will consist of a noninferiority evaluation of the D/C/F/TAF FDC tablet (investigational treatment arm) versus DRV/COBI FDC coadministered with FTC/TDF FDC (control arm), with respect to the proportion of subjects with HIV-1 RNA <50 copies/mL at Week 48 after the start of treatment in this study (as defined by the FDA snapshot analysis). It will be concluded that the D/C/F/TAF FDC tablet is not inferior to the control regimen if the lower bound of the 2-sided 95% confidence interval (CI) of the difference between treatment arms (D/C/F/TAF arm - control arm) in the response rate is greater than -10% (ie, a margin of 10% is applied to noninferiority assessment). The difference (with associated 95% confidence interval) will be constructed using the stratum-adjusted Mantel-Haenszel difference in proportions, where the stratification factors (HIV-1 RNA level [≤100,000 copies/mL] and CD4+ cell count [<200 cells/μL] or ≥200 cells/μL] at screening) determine the strata.

If noninferiority of the D/C/F/TAF arm to control arm is established, the lower bound of the 95% CI will be compared to 0; if the lower bound of the 95% CI is greater than 0, then superiority of D/C/F/TAF over the control arm will be established.

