## **Immunologic Change**

The changes from baseline in CD4+ cell count at Week 48, and 96 will be summarized using descriptive statistics. The differences in changes from baseline in CD4+ cell count at Week 48 between the 2 treatment arms and the associated 95% confidence intervals will be constructed using analysis of covariance (ANCOVA), including CD4+ cell count at baseline as continuous covariate in the model.

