## **Serum Creatinine and Cystatin C**

The changes from baseline in serum creatinine, eGFRcreatinine (by Cockcroft-Gault and by CKD-EPI) and eGFRcystatin (by CKPD-EPI) at Weeks 48 and 96 will be summarized by treatment arm and using descriptive statistics. The difference in changes from baseline at Week 48 in serum creatinine between the 2 treatment arms will be tested using ANCOVA, including baseline serum creatinine in the model.

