## **DXA Substudy – Bone Investigations**

Baseline, post-baseline, and the percent change from baseline at Weeks 24, 48, and 96 for selected bone biomarkers, including CTX, P1NP, PTH and 25-hydroxy vitamin D, will be summarized by treatment arm and visit using descriptive statistics. The within-treatment comparison will be done using the Wilcoxon signed-rank test. The comparison between the 2 treatment arms at Weeks 24 and 48 will be performed using the Wilcoxon rank-sum test.

Percent change from baseline in spine and hip BMD at Weeks 24, 48, and 96, as well as the change from baseline in BMD T-score will be summarized by treatment arm and visit using descriptive statistics. The between-treatment differences at Weeks 24 and 48 will be estimated using ANCOVA model, including baseline BMD value and other clinically relevant factors (if deemed necessary) in the model. The within-treatment comparison will be done using a paired t-test. A supportive longitudinal repeated measures analysis will be performed on this endpoint to obtain an estimate of the between-treatment difference along with its 95% CI at Week 48. This model will include post-baseline percent change from baseline as a response variable, terms for treatment, visit, the interaction of visit and treatment and the corresponding baseline BMD value as a covariate and other clinically relevant factors (if deemed necessary). An unstructured covariance matrix will be used to model the correlation among repeated measurements.

The BMD T-score will be summarized descriptively. BMD status based on the T-score (normal: ≥-1; osteopenia: from <-1 to -2.5; osteoporosis: <-2.5) will be tabulated.

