1. INTRODUCTION

This Statistical Analysis Plan (SAP) describes the Week 96 analysis that will be performed after the last subject enrolled in the open-label extension phase completes the Week 96 visit, or prematurely discontinues from the study. The final analysis will be described in a separate SAP.

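### Protocol Section 3.2 commits both randomisation factors as model covariates, but the Week 48 CD4 and serum creatinine ANCOVAs do not name them and the BMD models leave the choice open; a minor mismatch that costs nothing to repair

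*Protocol*

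**What the plan says.** Protocol Section 3.2, under control, blinding, randomisation and stratification, gives the two factors (HIV-1 RNA at or below versus above 100,000 copies/mL; CD4+ count below 200 versus at least 200 cells/μL, both at screening) and says they "will subsequently be used in the statistical analysis as covariates in the models". No endpoint is singled out and none is excepted.

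The analysis sections then read as follows.

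- **Primary endpoint (Section 11.4.1):** the difference is "constructed using the stratum-adjusted Mantel-Haenszel difference in proportions, where the stratification factors" define the strata. Section 11.4.2 applies the same method to the secondary snapshot and TLOVR proportions at Week 48.
- **CD4+ count, Week 48 (Section 11.4.2, Immunologic Change):** ANCOVA "including CD4+ cell count at baseline as continuous covariate in the model".
- **Serum creatinine, Week 48 (Section 11.6):** the between-arm difference "will be tested using ANCOVA, including baseline serum creatinine in the model".
- **BMD, Weeks 24 and 48 (Section 11.6, DXA substudy):** ANCOVA "including baseline BMD value and other clinically relevant factors (if deemed necessary) in the model". The supportive repeated-measures model has the same open-ended allowance.

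The synopsis describes the three ANCOVAs in the same terms. Section 11 adds that "Specific details will be provided in the Statistical Analysis Plan". The SAP supplied is for a later time point: "This Statistical Analysis Plan (SAP) describes the Week 96 analysis".

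**The concern.** Section 3.2 makes a general commitment, and no covariate model in the protocol names the factors it commits to. If they are left out, any part of the outcome that they explain stays in the residual variance, and the reported intervals and tests are somewhat less precise than they could be.

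The renal and bone comparisons are where this would be felt. Section 3.2 gives the direct TAF-versus-TDF safety comparison as a benefit of the chosen control. The bone substudy has its own power statement and enrols consenting subjects at selected sites. Randomisation is stratified for the whole trial, and the protocol describes no separate stratification by substudy participation. Balance on the two factors within about 170 subjects is therefore not assured, which matters if either factor predicts BMD change.

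For BMD, a covariate list left to later judgement also allows a choice that is better fixed before unblinding.

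**Working it through.** **1. The texts side by side.**

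| Analysis | Baseline outcome value | Both strata |
|---|---|---|
| Response proportions, Week 48 | not applicable | yes, as Mantel-Haenszel strata |
| CD4+ ANCOVA, Week 48 | yes | not named |
| Serum creatinine ANCOVA, Week 48 | yes | not named |
| BMD ANCOVA and repeated measures | yes | not named, not excluded |

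**2. What the supplied SAP adds.** Its Section 4.3.2.2 fits the Week 96 CD4+ and log10 HIV-1 RNA ANCOVAs separately in each arm, with only the reference value as covariate. Those models contain no between-arm contrast, so they neither repair nor repeat the Week 48 models. SAP Section 2.5 re-classifies both factors from baseline laboratory values and says the re-classified factors are the ones for analysis, without naming a model. Protocol Sections 3.2 and 11.4.1 refer to screening values.

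**3. The plan's own BMD figure.** Inputs from Section 11.3: 85 per arm, difference 2%, SD 4%, 1-sided alpha 2.5%.

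- SE = 4 × √(2/85) = 0.614
- Power = Φ(2/0.614 − 1.96) = Φ(1.30) = 90.3%

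The stated figure is 90%, so it reproduces (noncentral t gives 90.0%). It uses no covariate. The 95% half-width is 1.96 × 0.614 = 1.20 percentage points.

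**4. Effect of adding the strata.** The documents do not say how strongly the strata predict any of these outcomes, so partial R² (variance explained beyond the baseline value) is an assumption and a range is shown. For BMD the stated 4% is taken as the SD before the strata are added.

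- Narrowing of the interval = 1 − √(1 − R²). The degrees of freedom lost to two extra terms change this by about 0.01 percentage points, at N = 670 and at N = 170.
- BMD power = Φ(2/(0.614 × √(1 − R²)) − 1.96)

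| Assumed partial R² | Narrowing | BMD half-width | BMD power |
|---|---|---|---|
| 0 | 0% | 1.20 | 90.3% |
| 0.02 | 1.0% | 1.19 | 90.9% |
| 0.05 | 2.5% | 1.17 | 91.7% |
| 0.10 | 5.1% | 1.14 | 93.0% |

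**5. CD4+ count and validity.** A simulation of stratified 1:1 allocation was run with N = 670 and baseline CD4+ in the model. It assumed 20% of subjects above 100,000 copies/mL and a residual SD of 150 cells. Adding both strata narrowed the interval by 0%, 0.3%, 1.2% and 3.3% for assumed viral load effects of 0, 30, 60 and 100 cells. Coverage of the nominal 95% interval without the strata was 94.6% to 96.0%.

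**The case against.** The strongest reply is that omission from the Week 48 analysis itself is not shown. Section 11 presents itself as a general description and leaves specifics to the SAP, and the SAP holding the Week 48 between-arm models is not among the documents. Naming one covariate does not say that it is the only one. This stands, and it limits the point to the protocol text. It does not remove the mismatch there, since the general statement and the specific models sit in the same document.

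It can also be said that the strata may predict none of these outcomes. The documents show no link between either factor and creatinine or BMD change. For CD4+ count, the continuous baseline value already carries most of what the CD4+ stratum could add, leaving mainly viral load. This stands too: the gain could be zero. For creatinine the protocol describes only a test, so the gain there would be in sensitivity, with no stated interval to narrow.

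A reader might go further in three ways that the documents do not support:

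- That the BMD models exclude the strata. Their covariate list is open; the fair criticism is that it is not fixed in advance.
- That the analysis as a whole disregards the stratified design. The primary analysis and the secondary response proportions use both factors.
- That the intervals are wider than they need be as a matter of fact. That depends on a prognostic strength the documents do not give.

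**Conclusion.** The inconsistency is real and minor. It concerns the protocol's CD4+, serum creatinine and BMD models only. The non-inferiority conclusion is untouched, and omitting the strata does not invalidate the secondary comparisons; simulated coverage stayed close to 95%.

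The benefit of acting ranges from nothing, if the strata are not prognostic, to intervals about 5% narrower and BMD power of 93.0% instead of 90.3% at an assumed partial R² of 0.10. Smaller values of R² give 1% to 2.5%. The case for the change is that it honours the protocol's own statement and settles the BMD covariates beforehand at no cost. It does not rest on a demonstrated loss of precision.

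**What to change.** Add both stratification factors (HIV-1 RNA ≤100,000 or >100,000 copies/mL; CD4+ count <200 or ≥200 cells/μL) to the CD4+, serum creatinine and BMD ANCOVAs and to the BMD repeated-measures model. For BMD, name them in advance in place of the discretionary clause.

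State in the same place whether the screening values used at randomisation or the re-classified baseline values of SAP Section 2.5 apply, and use one definition throughout.

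If the strata are not wanted in these models, the alternative is to limit the Section 3.2 sentence to the stratified response analyses and still list the BMD covariates in advance.

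The cost is protocol and SAP wording. Both factors are already recorded for every randomised subject, so no new data or subjects are needed.
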